### 3.4 Duration of Follow Up

Patients will be followed for 7 days after each [F]F-AraG PET/MR imaging time point for safety assessment. Specifically, patients will be evaluated by telephone one day and one week after each radiopharmaceutical injection for safety follow-up. All adverse events will be recorded and graded according to CTCAE v4.0.

### 3.5 Subject Replacement

All patients who receive any dose [F]F-AraG of will be analyzed for safety. Subjects who discontinue from study participation prior to completing a second PET/MR scan will be replaced. Patients removed from study for unacceptable treatment related adverse event(s) will be followed until resolution or stabilization of all treatment related AEs to Grade 0-1.

[figure not shown]
## 4 Imaging Agent

[F]F-AraG is a radiopharmaceutical that will be produced under cGMP under the direction of [name]., in the Department of Radiology and Biomedical Imaging Radiopharmaceutical Facility. The radiopharmaceutical will be prepared in the same facility in which the injection and imaging will take place, the China Basin Imaging Center. In a prior study of 6 healthy volunteers imaged with [F]F-AraG, there were no Grade >1 adverse events related to tracer injection, and organ-specific dosimetry was within acceptable range.

[F]F-AraG will be administered by a licensed nuclear medicine technologist under the supervision of a physician boarded in nuclear medicine on an outpatient basis. It will be administered at a single time point intravenously prior to PET imaging, at a subpharmacologic, tracer microdose consistent with imaging practices. The one-time nominal injected dose will be less than or equal to 5.7 mCi for male patients and less than or equal to 4.4 mCi for female patients. A simultaneous whole body MRI (PET/MR) will be used for attenuation correction and anatomic localization of [F]F-AraG uptake and SUV calculation. Each [F]F-AraG injection will be followed by a whole body PET/MR acquisition, immediately followed by a limited PET/MR acquisition that includes only the pelvic region. The patient will not need to be repositioned between the acquisitions. The limited PET/MR dedicated pelvic region acquisition will not add any additional radiation exposure, and will require only 5-10 additional minutes. Each probe injection plus PET/MR imaging session (on and off the scanner) is estimated to last approximately 60 to 90 minutes.

Patients will be asked to drink 16 ounces of water approximately 30 minutes prior to furosemide (Lasix) administration. 20 mg Lasix will be administered intravenously 10-30 minutes prior to injection of radiopharmaceutical. The patient will void 30 to 45 minutes after Lasix administration. PET/MR imaging will then be performed from the bottom up so that the surrounding tissues is optimally visualized. After completion of the whole body imaging, a repeat 3-minute tumor image will be acquired at the end of imaging.

**Figure 4:** Bladder tumor visualization with [F]FDG. (A) No Lasix administration. (B) Patient with exophytic bladder mass with Lasix administration at time of tracer injection. (C) Patient with bladder thickening with Lasix administration at time of tracer injection.

## 5 Study Procedures and Observations

A written, signed, informed consent form (ICF) and a Health Insurance Portability and Accountability Act (HIPAA) authorization must be obtained before any study-specific assessments are initiated. A copy of the signed ICF will be given to the subject and a copy will be filed in the medical record. The original will be kept on file with the study records.

### 5.1 Study Assessments

The Screening procedures and assessments must be completed within 28 days of the day 1 Visit unless otherwise noted (i.e., baseline staging scans).

- Vital signs
- Height and weight
- Physical examination and medical history
- Performance status
- Baseline staging scans with CT chest, head, and/or neck + CT or MRI of the abdomen/pelvis ± bone scan within 42 days of study enrollment
  - Patients may receive staging scans and [F]F-Ara PET/MR imaging on the same day if the patient meets eligibility criteria for the study as assessed by Principal Investigator prior to the completion of the scan.
- MRI screening form (Appendix 4)
- Tissue collection
  - Archival tumor tissue from biopsy or resection will be collected for all patients.
- Baseline labs performed during screening window of Day -28 to Day +1
  - CBC with differential\*
  - BMP\*
  - Urinalysis\*
  - Pregnancy test for women of childbearing potential\*

\*If already performed in the screening window (e.g. during screening for corresponding neoadjuvant atezolizumab study protocol), will not need to be repeated.

### 5.2 Study Procedures

[F]F-Ara experimental PET radiopharmaceutical (hereafter referred to as “radiopharmaceutical”)

- Vital signs and EKG will be recorded before and after completion of imaging.
- Administration of Furosemide (Lasix)
  - Patients who are not eligible to receive Lasix are excluded from this study (Section 3.3.2).

- Because [F]F-AraG is renally excreted with uptake in the urine, patients will be encouraged to drink 16 ounces of water approximately 30 minutes before furosemide (Lasix) administration, and will receive 20 mg of Lasix intravenously within 10-30 minutes prior to injection of the radiopharmaceutical.
- Patients will void 30 to 45 minutes after Lasix administration. PET/MR imaging will then be performed from the bottom up so that the surrounding tissue is optimally visualized.
- A Foley catheter may be placed if Lasix diuresis and voiding fails to provide adequate image quality.
- [F]F-AraG PET/MR imaging
  - Patient shall begin imaging between 1 to 180 minutes after the injection of the radiopharmaceutical. Coverage for the scan will extend from the top of the patient's head through the toes.
  - Each [F]F-AraG injection will be followed by a whole body PET/MR acquisition, immediately followed by a limited PET/MR acquisition that includes only the targeted tumor region. The patient will not need to be repositioned between the acquisitions. The limited PET/MR dedicated target region acquisition will not add any additional radiation exposure, and will require only 5-10 additional minutes.
  - Simultaneous whole body MRI (PET/MR) will be performed for attenuation correction.
  - Each probe injection plus PET/MR imaging session (on and off the scanner) is estimated to last approximately 60 to 90 minutes.
  - No formal report of the findings from imaging studies will be created. Each study will be reviewed by a board certified nuclear medicine physician and radiologist within one week after completion of the study. An expert molecular imaging investigator will analyze all data.
    - Exception: If an acute and new finding is found on MRI, this finding will be reported and documented, and the investigator will be notified.

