Duration of Therapy	
Each patient will undergo two PET/MR imaging scans. The first imaging will be performed within 7 days of starting anti-PD-1 or anti-PD-L1 (baseline). The second imaging will be performed within 7 days before surgery in the neoadjuvant cohort, and between C1D15 and C2D7 anti-PD-1 or anti-PD-L1 in the SOC cohort. A bolus injection of [F]F-AraG will be administered at each imaging time point. Each injection will be followed by up to two whole-body PET/MR scans. Each probe injection plus PET/MR imaging session is estimated to last up to three hours.

Duration of Follow up	
All patients will be followed for 7 days after each [F]F-AraG PET/MR imaging time point for safety assessment.

[figure not shown]
Duration of study	The study is anticipated to reach completion 20 months from the time the study opens to accrual.
Study Drugs	2'-deoxy-2'-[  F]fluoro-9-β-Darabinofuranosylguanine ([  F]F-AraG) is a radiopharmaceutical imaging agent that will be produced under CGMP (Current Good Manufacturing Practice) regulations under the direction of [name] in the Department of Radiology and Biomedical Imaging Radiopharmaceutical Facility at UCSF. A one-time nominal injection dose of ≤5.7mCi for male subjects and ≤4.4mCi for female subjects will be administered at each imaging time point. A simultaneous whole body MRI will be used for attenuation correction and anatomic localization of [  F]F-AraG uptake and SUV calculation.
Safety Assessments	Patients will be evaluated one day and one week via telephone visit after each radiopharmaceutical injection for safety follow-up. All adverse events will be recorded. Due to the noninvasive and non-therapeutic nature of the study, potential risks of the study are anticipated to be low.
Unique Aspects of this Study	To our knowledge, this is the first study to investigate changes in activated T cell localization in the setting of immunotherapy for cancer utilizing functional PET imaging.

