## **8 Statistical Considerations and Image Analysis**

### **8.1 Image Processing and Analysis**

Trained nuclear medicine physicians and molecular imaging scientists will evaluate the reconstructed PET, PET/MR images using a PET volume computer-assisted reading software package. Volumetric regions of interest will be chosen around tumors based on anatomic (MR) images and activity within the tumor will be expressed in a standardized uptake value (SUV) format where SUV will be defined as [concentration of tracer in tumor]/(injected dose/body weight). Tumor SUV at baseline (before anti-PD-1 or anti-PD-L1 treatment) will be compared with the post-therapy values to determine the change in SUV associated with the therapy. Whole body images will be analyzed to determine differences in tracer distribution relative to pre/post therapy and versus the normal subject pool already studied.

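### Scans may start 1 to 180 minutes after injection and a patient's two scans need not match, so start-time differences can distort the 2-fold SUVmax rule

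*Combined protocol and SAP*

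**What the plan says.** On the start of imaging, section 5.2 gives one rule for either visit: "Patient shall begin imaging between 1 to 180 minutes after the injection of the radiopharmaceutical".

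Other text bears on the start time only indirectly:

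- Sections 4 and 5.2 give furosemide 10-30 minutes before injection. Section 5.2 continues: "Patients will void 30 to 45 minutes after Lasix administration. PET/MR imaging will then be performed from the bottom up".
- Session length in section 5.2, and in the same terms in section 4: "Each probe injection plus PET/MR imaging session (on and off the scanner) is estimated to last approximately 60 to 90 minutes".
- Session length in the Abstract (Duration of Therapy): "Each probe injection plus PET/MR imaging session is estimated to last up to three hours".

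Section 8.1 states that "SUV will be defined as [concentration of tracer in tumor]/(injected dose/body weight"), a formula with no uptake-time term, and compares baseline with post-therapy values directly. Sections 8.2 and 8.4 classify each patient by whether post-treatment SUVmax is at least twice baseline. Cohort 2 stops if there are no doublings in 8 patients and rejects the null with 2 or more in 19.

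The acquisitions are described in different ways. The Abstract says "Each injection will be followed by up to two whole-body PET/MR scans". Section 4 has a whole-body acquisition, "immediately followed by a limited PET/MR acquisition that includes only the pelvic region", and then says that "a repeat 3-minute tumor image will be acquired at the end of imaging". Section 5.2 has a whole-body acquisition followed by a limited one of the targeted tumour region. None is named as the source of SUVmax.

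**The concern.** The decision variable is a within-patient ratio with a hard cut at 2. A ratio of two scans cancels what the scans share, but uptake time need not be shared. One patient could be scanned early at baseline and late after treatment, and another the reverse, both in full compliance. If tumour SUV rises or falls with time after injection, part of the ratio reflects the clock.

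Two errors are then possible. A true doubling can read below 2, which costs power and makes a stage 1 stop more likely. Or a patient with no change can read above 2. Because the null rate is only 1% and two doublings in 19 are enough to reject, the second error needs few patients to matter. Without matched times, or recorded times to adjust for, a reader could not tell a timing effect from T-cell activation, which is what the study sets out to measure.

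**Working it through.** **Step 1. Reproduce the Cohort 2 design.** Inputs from section 8.2: 8 patients then 11 more, stop at 0 of 8, reject at 2 or more of 19, null 1%, alternative 20%. With p the probability that a patient is observed to double and q = 1 − p, rejection fails if there are no doublings in the first 8, or exactly one in the first 8 and none in the next 11:

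P(reject) = 1 − q^8 − 8·p·q^18.

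- p = 0.20: 1 − 0.1678 − 0.0288 = 0.803. The stated 80% power is reproduced.
- p = 0.01: 1 − 0.9227 − 0.0668 = 0.0105. The stated 0.05 is a ceiling, not the attained value.

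**Step 2. Sensitivity of the rule (exact, no kinetic assumption).** By total observed doubling rate, true and false together:

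| Observed rate | P(reject) |
|---|---|
| 1% | 0.0105 |
| 2% | 0.038 |
| 2.33% | 0.05 |
| 3% | 0.078 |
| 5% | 0.178 |

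If false doublings come on top of the 1% null, a 2% false rate gives p = 0.01 + 0.99 × 0.02 = 0.0298 and P(reject) about 0.077. A 5% false rate gives p = 0.0595 and about 0.23.

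**Step 3. What the other text implies for the start.** Take injection as time 0. Furosemide is at −30 to −10 minutes and the void 30-45 minutes later, so the earliest void is −30 + 30 = 0 and the latest is −10 + 45 = +35 minutes. Imaging follows, with no time given. This does not exclude early starts. At the late end, a start near 180 minutes does not fit a 60-90 minute session that includes injection, and leaves no scanning time in a three-hour one.

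**Step 4. Illustration only: timing alone.** The documents contain no tumour time-activity data, so the following is assumed: SUV proportional to t^b, no other noise, and both starts independent and uniform on a window L to U. The timing ratio is (t2/t1)^b. A true 2.5-fold rise reads below 2 when t2/t1 < r with r = 0.8^(1/b). A false doubling needs t2/t1 ≥ 2^(1/b), which by symmetry has the same probability as t2/t1 ≤ r with r = 0.5^(1/b). In both cases, when rU > L,

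P = (rU − L)² / [2r(U − L)²], and otherwise P = 0.

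Example, 30-90 minutes and b = 0.5: r = 0.64, so P = (57.6 − 30)² / (2 × 0.64 × 3600) = 761.8/4608 = 16.5%.

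| b | 0.1 | 0.2 | 0.3 | 0.5 |
|---|---|---|---|---|
| 30-90 min: 2.5-fold rise hidden | 0 | 0 | 4.8% | 16.5% |
| 30-90 min: false doublings | 0 | 0 | 0 | 0 |
| 30-90 min: power at a 20% true rate | 0.803 | 0.803 | 0.782 | 0.718 |
| 1-180 min: 2.5-fold rise hidden | 4.9% | 16.0% | 23.5% | 31.8% |
| 1-180 min: false doublings | 0 | 1.1% | 4.5% | 12.1% |

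The power row puts p = 0.20 × (1 − hidden) into step 1; for b = 0.5, p = 0.167 gives 0.718. A true rise of exactly 2-fold is hidden in half of pairs under any independent mismatch, because t2 < t1 half the time.

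**Step 5. Effect of matching.** Take baseline starts of 30-90 minutes, the second scan within ±10 minutes of the first, and |b| up to 0.5. The extreme time ratios are 20/30 and 40/30. The largest timing ratio is (30/20)^0.5 = 1.22, below 2, so there are no false doublings. The smallest is (20/30)^0.5 = 0.816, and 2.5 × 0.816 = 2.04, so no 2.5-fold rise is hidden.

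Cohort 1 states no rejection count, so the same calculation cannot be made for it.

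**The case against.** The strongest defence is that the practical window is narrower than 1-180 minutes, that one imaging facility will tend to scan at similar times, and that the effect depends wholly on kinetics the documents do not give. That stands as a limit on size: with b at or below 0.2 and 30-90 minute starts, the model shows no effect on a 2.5-fold rise. But habit is not a protocol rule. The void sequence does not remove early starts, and the 30-90 minute window is itself an assumption.

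A second defence is that this is a pilot with a descriptive primary endpoint (section 2.2.1), and that section 8.4 provides for re-evaluating the imaging protocol after a null first stage. This also stands in part. For the paired Wilcoxon test in section 8.5, independent start times add noise but no direction. Even so, sections 8.2 and 8.4 make a formal decision on the count of doublings, and re-evaluation comes only after that count.

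The amendment requirement in section 9.4 gives no protection, since moving a start within 1-180 minutes changes nothing in the protocol.

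Two stronger readings are tempting and unsupported. A reader might infer that Cohort 2's type I error is in fact inflated. That would need tumour kinetics and actual start times, and the documents give neither. A reader might also infer that uptake times will go unrecorded. The documents are only silent on recording.

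**Conclusion.** The omission is real and worth correcting, as an inexpensive improvement rather than a fatal flaw. What is certain is that the permitted window is wide, the two scans are not matched, SUV has no time term, and the Cohort 2 rule passes 0.05 once the observed doubling rate reaches 2.33%. What is conditional is how far timing moves that rate. The model figures rest on an assumed power-law curve, independent uniform starts and assumed windows, and they range from no effect to a substantial one. Hiding true rises needs only a modest mismatch. False doublings need very early or widely spread starts.

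The conflict between the late end of the window and the stated session lengths needs reconciling whatever the kinetics. The differing acquisition descriptions are a secondary drafting matter.

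**What to change.** - **Section 5.2:** replace the 1-180 minute window with one target uptake time chosen by the imaging investigators. Require each patient's second scan to start within a fixed tolerance (for example ±10 minutes) of that patient's own baseline uptake time. Record injection-to-scan time at both visits.
- **Abstract and sections 4 and 5.2:** reconcile the start window with the session lengths, reconcile the acquisition descriptions, and take SUVmax from the same named acquisition at both visits.
- **Section 8.5:** add a sensitivity analysis that repeats the responder count without out-of-tolerance pairs. Those pairs stay in the main count.
- **Unchanged:** the 2-of-19 rule, its denominator and the sample size.

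The cost is protocol wording, less scheduling flexibility on the scanner, and an occasional out-of-tolerance pair.

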### 5.3 Follow Up Procedures

Patients will be evaluated one day and one week by telephone after the radiopharmaceutical injection for safety follow-up. All adverse events will be recorded.

- Cohort 1 (neoadjuvant cohort): Following completion of neoadjuvant atezolizumab cycles per corresponding study protocol, the patient will return for repeat imaging within 7 days of undergoing surgery.
- Cohort 2 (SOC cohort): Between Cycle 1 Day 15 and Cycle 2 Day 7 anti-PD-1 or anti-PD-L1, the patient will return for repeat imaging.

### 5.4 Prohibited Medications

Patients should receive no systemic therapy for their cancer other than anti-PD-1 or anti-PD-L1 prior to completion of the two planned [F]F-AraG PET scans.

## 5.5 Safety

Patients will be evaluated via telephone on the day after and at one week after each radiopharmaceutical injection for safety follow-up. All adverse events will be recorded. For patients in the neoadjuvant cohort (Cohort 1), the principle investigator and study personnel (e.g. clinical research coordinator) of the corresponding neoadjuvant atezolizumab study will also be informed of the [F]F-AraG PET/MR imaging dates for each patient, and will follow up with any adverse events related to imaging during subsequent study clinic visits (e.g. Cycle 1 Day 1 visit after baseline imaging).

Potential risks of the study are anticipated to be low. Should a patient experience a Grade 1 or Grade 2 adverse event at the time of baseline scan which subsequently resolves, he/she may proceed with undergoing the second (pre-surgery) PET/MR imaging.

In the situation that a patient experiences a Grade 3 or higher adverse event at the time of baseline scan, the study should be permanently discontinued for that patient. The study will be halted after one serious adverse reaction attributable to [F]F-AraG is seen or if over 20% of patients experience Grade 3 or higher toxicities for re-evaluation of tracer dose (Section 8.4).

## 6 Study Calendar

	Screening (Day -28 to 1)	First (baseline) imaging			Second imaging		
		Day 1 (Image)	Safety Follow Up		Day 1 (Image)	Safety Follow-Up	
			Day 2 (Tele)	Day 8 (Tele)		Day 2 (Tele)	Day 8 (Tele)
Informed consent	X						
Medical history	X						
Physical exam	X						
Performance status	X						
Baseline staging scans 	X						
Height	X						
Weight	X						
Vitals 	X	X			X		
Pregnancy test 	X						
CBC, BMP and UA 	X						
MRI screening form 	X						
Tissue collection 	X						
Furosemide (Lasix) 		X			X		
[  F]F-AraG PET/MR imaging 		X			X		
Electrocardiogram 		X			X		
AE Assessment 		X	X	X	X	X	X

 Patients may receive staging scans and [F]F-Ara PET/MR imaging on the same day if the patient meets eligibility criteria for the study as assessed by Principal Investigator prior to the completion of the scan.

 Vitals consist of heart rate, blood pressure, blood oxygen %, temperature, and respiratory rate. On imaging days, vitals are collected before and after imaging.

 Pregnancy tests are performed for women of childbearing potential.

 Screening labs, including CBC with differential, BMP and urinalysis are required if not already performed by the corresponding neoadjuvant atezolizumab study protocol or SOC.

 The study investigator will review the UCSF MRI screening form to confirm no contraindication to MRI imaging.

 Archival tissue from tumor resection or biopsy should be of good quality based on total and viable tumor contents. Fine-needle aspiration, brushing, and cytologic cell pellets are not acceptable.

 Patients will be encouraged to drink 16 ounces of water approximately 30 minutes before furosemide (Lasix) administration, and will receive 20 mg of Lasix intravenously within 10-30 minutes prior to injection of the radiopharmaceutical. Patients will void 30 to 45 minutes after Lasix administration before PET/MR imaging.

 PET/MR imaging will be performed from the bottom up so that the surrounding tissues is optimally visualized.

 Electrocardiograms are assessed before and after imaging. Adverse events are assessed by a physician on the research team after imaging.

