The first-in-human study of [F]F-AraG was performed at UCSF in 2015 (Yaghoubi S et al., 2015). [F]F-AraG was administered at a subpharmacologic, tracer microdose consistent with imaging practices in six healthy volunteers (3 males and 3 females). The distribution of the tracer was evaluated over the first 4 hours after injection. A representative whole body PET/MR image in a healthy volunteer is shown in **Figure 3**. The tracer was well tolerated by all patients and there were no > Grade 1 adverse events. The only AE that occurred in more than one volunteer was positive WBC esterase in the urinalysis without urinary symptoms. Normal uptake was seen in the clearance organs: liver, kidneys and bladder. There appeared to be uptake in the thyroid and parotid glands, as well as limited accumulation in the cardiac muscle. In these first-in human studies, no additional drugs were administered to subjects as the biodistribution was determined

for radiation dose estimates. However, in the present study, oral fluid intake and a diuretic (furosemide) will be administered for subjects to allow rapid clearance of the excreted radiotracer from the renal collecting systems and to provide diluted radiotracer within the background of the bladder, and to enable clear evaluation of distribution of the radiopharmaceutical in the walls of the ureters, bladder, and surrounding structures.

[figure not shown]

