### 3.3 Eligibility Criteria

Patients must have baseline evaluations performed prior to the first injection of [F]F-AraG and must meet all inclusion and exclusion criteria. In addition, the patient must be thoroughly informed about all aspects of the study, including the study visit schedule and required evaluations and all regulatory requirements for informed consent. The written informed consent must be obtained from the patient prior to enrollment. The following criteria apply to all patients enrolled onto the study unless otherwise specified.

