### 7.3 Definition of Adverse Events

#### 7.3.1 Adverse Event

An adverse event (also known as an adverse experience) is defined as any untoward medical occurrence associated with the use of a drug in humans, whether or not considered drug related. More specifically, an adverse event (can be any unfavorable and unintended sign (e.g., an abnormal laboratory finding), symptom, or disease temporally associated with the use of a drug, without any judgment about causality. An adverse event can arise from any use of the drug (e.g., off-label use, use in combination with another drug) and from any route of administration, formulation, or dose, including an overdose.

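### No required assessment after either injection includes a laboratory test, so few or no laboratory adverse events in the safety table would not be evidence of safety

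*Combined protocol and SAP*

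**What the plan says.** **Laboratory tests.** In the Section 6 calendar, CBC, BMP and urinalysis share one row with a single mark, under Screening. The footnote reads "Screening labs, including CBC with differential, BMP and urinalysis are required if not already performed by the corresponding neoadjuvant atezolizumab study protocol or SOC". Section 5.1 gives the same timing: "Baseline labs performed during screening window of Day -28 to Day +1". Section 3.3 adds "Patients must have baseline evaluations performed prior to the first injection of" the tracer.

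**After each injection.** Sections 5.2 and 6 require vitals and an ECG before and after imaging, and a physician's adverse-event assessment after imaging. Section 3.4 then states that "patients will be evaluated by telephone one day and one week after each radiopharmaceutical injection for safety follow-up". For Cohort 1 only, Section 5.5 has the companion-trial team told of the imaging dates, so that it can follow up imaging-related events at its own clinic visits. The example given is the Cycle 1 Day 1 visit after baseline imaging.

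**What counts and what is recorded.** The definition in Section 7.3.1 includes "an abnormal laboratory finding". Sections 3.4, 5.3 and 5.5 say every adverse event is recorded. Section 7.4 opens by saying that events of Grade 3 and above are recorded.

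**Earlier human experience.** Section 1 reports on six healthy volunteers: "The tracer was well tolerated by all patients and there were no > Grade 1 adverse events". It continues: "The only AE that occurred in more than one volunteer was positive WBC esterase in the urinalysis without urinary symptoms".

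**The concern.** The protocol defines a class of adverse event, promises to record all events, and cites an example of that class from the tracer's first-in-human study. It then schedules no test that could show such an event after tracer is given. A urinalysis change without symptoms will not come up in a telephone call, and vitals, an ECG and a same-day clinical check do not test urine or blood.

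What is at stake is how the safety table is read. If it shows few or no laboratory events, a reader may take that as information about the tracer when it mainly reflects that nobody looked. The only earlier human exposure described in the protocol is six volunteers, so this table will carry weight when later studies of the agent are planned.

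**Working it through.** The plan states no figure on this point, so there is none to reproduce. The check sets the schedule beside the definitions.

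**1. Required contacts after an injection (Sections 3.4, 5.2, 5.3, 5.5, 6).**

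| Contact | Content | Laboratory test |
|---|---|---|
| Imaging day | Vitals, ECG, physician adverse-event assessment | None |
| Day 2 | Telephone | None |
| Day 8 | Telephone | None |

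The pattern is the same for both injections: 3 contacts × 2 = 6 per patient, with 0 laboratory tests. With 31 patients (Section 3.2) there are 31 × 2 = 62 planned injections and 0 required post-injection tests. Nor is any test required between the two injections.

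**2. Could the screening sample serve as a post-injection test?** Section 5.1 lets the window run to Day +1, the calendar heading runs from Day -28 to Day 1, and the calendar labels the baseline imaging day Day 1. Section 3.3, however, puts baseline evaluations before the first injection. Even on the loosest reading there is one sample per patient. If it were taken after injection, there would be no earlier sample required by this protocol to compare it with. It is a baseline, not a safety test.

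**3. Could another route supply the result?**
- Cohort 1 (12 patients): the companion-trial visits in Section 5.5. These documents specify no CBC, BMP or urinalysis for those visits.
- Cohort 2 (19 patients): no comparable arrangement; Section 5.5 names Cohort 1 only.
- Either cohort: tests drawn for treatment reasons may exist. Section 7.3.1 does not limit the source of a laboratory finding, so such a result would count if the team learned of it. No section provides for retrieving it.

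**4. Would a low-grade finding be recorded if it were found?** Sections 3.4, 5.3 and 5.5 say yes. The opening sentence of Section 7.4 sets Grade 3 and above, although the same section goes on to give grade definitions from 0 to 5. Appendix 2 uses Grades 3 to 5 for entry into the trial management system. Under the narrower wording a Grade 1 urinalysis finding might not be recorded even when known.

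**5. What the earlier study supports.** More than one of six means at least 2/6 = 33%. The exact count, any attribution to the tracer and the volunteers' baseline urinalyses are not given. This shows that a symptomless laboratory event has been seen in people given the tracer. It does not give a usable rate for this trial.

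**The case against.** The strongest reply is that a light laboratory schedule is a reasonable choice for an imaging agent given at a microdose. No earlier event exceeded Grade 1. Safety is not a listed objective or endpoint in Section 2. The rules in Sections 5.5 and 8.4 turn on serious reactions or Grade 3 and higher toxicity. Follow-up is more than telephone calls, since a physician assesses each patient after imaging and Cohort 1 has companion-trial visits. All of this stands, and it keeps the point small. It does not answer the reporting problem, because none of those contacts includes a specified laboratory test.

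Several stronger readings are tempting, and the documents do not support them.

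- **That such events cannot be seen at all.** Companion-trial or routine tests may show them by chance. How often depends on practice that these documents do not describe.
- **That a number of missed cases can be projected.** Taking 2/6, with exact 95% interval 4.3% to 77.7%, and multiplying by 31 gives about 10, with a range of 1 to 24. That range excludes almost nothing. It also carries an unattributed minimum count from healthy volunteers over to cancer patients, some with bladder tumours.
- **That blood counts are a particular worry.** Section 1 describes the compound as toxic selectively to T cells, but Sections 1 and 4 place the dose below pharmacological effect, and Section 1 reports no blood-count event.
- **That the calendar footnote already allows later results to be imported.** It only waives a repeat of the screening tests.
- **That the stopping rule is disabled.** A silent Grade 3 laboratory change would not reach Section 8.4 through a scheduled test, but the documents give no sign of such an event, and the known finding was at most Grade 1.

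**Conclusion.** The gap is confirmed: 0 required laboratory tests after either injection, against a definition that includes laboratory findings, a promise to record all events, and a recurrent symptomless urinalysis finding in the earlier study. A small laboratory count in the safety table should therefore not be read as evidence of safety.

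This is a limitation of ascertainment and an inexpensive improvement. It does not touch the primary endpoint, the interim decision for Cohort 2 or the sample size. The conclusion rests on the schedule as written. It assumes that no other document, such as the companion protocol or a data-collection manual, already brings post-injection laboratory results into this trial's database.

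**What to change.** 1. In Section 5.3 and the calendar, add abstraction of any CBC, BMP and urinalysis already obtained at companion-trial or standard-of-care visits after each injection. Cycle 1 Day 1 after baseline imaging is one such visit.
2. In the safety table, show shifts from screening with attribution, and give the number of patients who had a post-injection result for each test. That denominator lets a reader separate a normal result from an absent one.
3. State in the report that laboratory adverse events were otherwise not systematically ascertained.
4. Reconcile Section 7.4 with Sections 3.4, 5.3 and 5.5 on which grades are recorded. Otherwise a Grade 1 finding obtained under item 1 might still go unrecorded.

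**Cost.** Some abstraction work, and no new procedure for the patient. Attribution will be difficult: disease and the antibody are competing causes, and in Cohort 1 surgery follows the second scan within 7 days. Urinalysis may often be missing from routine visits, which is why the denominator in item 2 matters.

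An added urine test at the imaging visit is not recommended here. It would be an extra procedure on a void deliberately diluted by water and furosemide, compared with a screening sample taken up to 28 days before without that preparation.
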